#### **Specific Aim 2: To determine if, and which, maternal side effects are more common at 1 hour, 4 hours, and time of delivery with an alternate magnesium sulfate dosing protocol in obese women.**

## Hypotheses

We hypothesize that a randomized trial of alternate dosing of intravenous magnesium in obese women will allow us to:

1. Determine optimal antenatal magnesium dosing protocols to optimize therapeutic serum magnesium levels in obese preeclamptic women.
2. Determine significant covariates and correlations between maternal serum magnesium levels and maternal side effects and outcomes.
3. Determine the optimal antenatal magnesium dose to minimize adverse drug effects while maintaining a therapeutic serum magnesium level in the mother.

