## **Study Design**

The proposed study would use 1:1 allocation to randomize women with a  $\text{BMI} \geq 35 \text{ kg/m}^2$  treated with magnesium sulfate for preeclampsia to either standard dosing of the drug at OHSU (4g loading dose, followed by a 1 g/hr infusion) or to increased dosing (6g loading dose, followed by a 2 g/hr infusion). Maternal serum magnesium levels will be obtained at baseline, as well as after administration of magnesium sulfate at 1 hour, 4 hours, and at the time of delivery (within 20 minutes). We will exclude patients who are  $< 32$  weeks gestation, as these women will automatically be administered a 6g loading dose, followed by 2g/hr infusion for fetal neuroprotection. The outcome will be a comparison of the proportion of preeclamptic women in each magnesium sulfate protocol group who have therapeutic serum levels 4 hours after administration, and at the time of delivery (serum magnesium level of  $\geq 4.8$  mg/dL). We hypothesize that a significantly higher proportion of women with a  $\text{BMI} \geq 35 \text{ kg/m}^2$  will be subtherapeutic at 4 hours and at the time of delivery when administered standard dosing of magnesium sulfate. Findings from the proposed research can be used to tailor treatment for preeclampsia in obese pregnant patients.

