## **2. Procedures Involved**

After obtaining informed consent, the subject will be randomly assigned to one of two treatment groups: 1.) a starting dose of magnesium sulfate of 4g, followed by 1g every hour until 24 hours after delivery (the current standard regimen used at OHSU), or 2.) a starting dose of magnesium sulfate of 6g, followed by 2g every hour until 24 hours after delivery. There will not be a placebo arm of the study; only a smaller dose or larger dose of magnesium sulfate administered. Although the study dosing is randomized, it is not blinded and both the investigator and the research subject may know what dose of magnesium sulfate is being administered. If the subject is found to be symptomatic at any point in the study, the usual clinical care will be provided, which would include checking a serum magnesium level and decreasing the dose of magnesium sulfate, if needed. Study participation will continue; however, the timing and details of the dosing change will be recorded and used for research purposes.

If there is an indwelling intravenous catheter in place for surgery, we will attempt to use it to draw blood. We will draw a sample from a vein if we are not able to collect the samples from an existing intravenous catheter.

Specimens will be collected as follows:

- Serum magnesium before the administration of magnesium sulfate
- Serum magnesium at 1 hour, 4 hours, and delivery after the initial dose of magnesium sulfate
- Each sample will be 5-10 ml (approximately 1-2 teaspoon). The total drawn for all samples will likely not exceed 5 teaspoons.
- Urine samples will be obtained if possible at these same time points.
- If the patient requires spinal anesthesia for cesarean delivery, 0.5 ml (a few drops) of spinal fluid will be taken to check for magnesium levels at the same time the spinal anesthetic is being performed.

	Visit 1 Day 1	Visit 2 Day 1	Visit 3 Day 1	Visit 4 Day 1
Consent Discussion, Screening tests and medical history	X			
Blood draw (1 teaspoon)	X	X	X	X
Urine sample (2 teaspoons)	X	X	X	X
Time (after magnesium sulfate administration)	baseline	1 hour	4 hours	Time of delivery (within 20 mins)

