**Information that may be abstracted from the subject's chart includes** maternal age, race, height, weight, renal function and creatinine clearance (if available), maternal heart rate variability, medical comorbidities, chorioamnionitis, labor duration, mode of delivery, gestational age, cord pH, and birthweight. These covariates may be considered in the pharmacokinetic model. These covariates demonstrate biological plausibility, and have physiologic potential to significantly impact the optimal dosing of magnesium. Additionally, maternal side effects (flushing, sedation, nausea, vomiting, respiratory rate, oxygen saturations, blood pressure, heart rate, and patella tendon reflex depression) will be assessed prospectively by a physician or research assistant at the same time-points as the PK sampling. Neonatal data will include NICU admission, need for respiratory support, need for blood pressure support, electrolyte abnormalities, feeding difficulties, intraventricular hemorrhage, necrotizing enterocolitis, seizures, sepsis, respiratory distress syndrome, retinopathy, patent ductus arteriosus, fetal/infant death.

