**4. Data Analysis**

Univariate and multivariate mixed-effects modeling will be utilized to assess the impact of various covariates on the outcome of serum magnesium level at different time points after magnesium sulfate administration. As previously described, assuming 95% of normal weight women have therapeutic serum magnesium levels after 4 hours of administration, we anticipate that 18 patients (36 total) are needed in each dosing group to detect a 50% difference in the proportion of women with a  $\text{BMI} \geq 35 \text{ kg/m}^2$  who have therapeutic magnesium levels 4 hours after magnesium sulfate administration. Based on current patient load, which includes treatment of approximately 40 preeclamptic patients per month, and the additional inclusion criteria of the disease severity requiring magnesium sulfate administration, as well as a maternal  $\text{BMI} \geq 35 \text{ kg/m}^2$ , and anticipated number of patients declining study participation, we anticipate potential enrollment of 1-2 patients per week.

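### Specific Aim 2 compares side effects after dosing and gives no role to the pre-dose assessment, so symptoms already present would shrink the difference between arms

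*Combined protocol and SAP*

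**What the plan says.** Specific Aim 2 asks whether, and which, "maternal side effects are more common at 1 hour, 4 hours, and time of delivery" with the alternate regimen. It names three times, all after dosing.

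The chart-abstraction paragraph of Section 2 (Procedures Involved) lists "maternal side effects (flushing, sedation, nausea, vomiting, respiratory rate, oxygen saturations, blood pressure, heart rate, and patella tendon reflex depression" and says these "will be assessed prospectively by a physician or research assistant at the same time-points as the PK sampling". The specimen list in the same section begins with "Serum magnesium before the administration of magnesium sulfate", and the visit table has a baseline column. Taken together, these place a side-effect assessment before the first dose, although only by cross-reference.

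Section 4 (Data Analysis) names one method, mixed-effects modeling to "assess the impact of various covariates on the outcome of serum magnesium level at different time points after magnesium sulfate administration". It gives no method for side effects. The documents contain no new-or-worsened definition, no change from baseline, no baseline adjustment, no attribution rule and no cut-off for the vital signs.

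**The concern.** Nausea, vomiting and sedation can be present before magnesium in women who are in labor or have preeclampsia. If Aim 2 is analyzed as the share of women with each symptom at each later time, those cases enter both arms alike. They tell us nothing about the dose, yet they pull the two proportions together.

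Aim 2 is the only stated aim that compares maternal harm between the regimens, and the third hypothesis is about limiting adverse drug effects. The loss therefore falls on the harm side of the question, in a trial whose 18 women per arm were chosen for Aim 1. The reading that would reduce the loss appears to be collected already.

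**Working it through.** **The plan's own figure.** Number of Subjects gives 18 per arm, for therapeutic magnesium at four hours. Alpha, power and sidedness are not stated. Assuming two-sided 5%, 50% versus 95% needs 19 per arm (80% power, continuity correction), 17 (85%, no correction) or 19 (90%, no correction). A 50-point difference taken as 45% versus 95% needs 18 (85%, with correction). So 18 is reproducible to within one or two women, and this point does not dispute it. No figure is given for Aim 2.

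**Inputs.** The 18 per arm comes from the plan. The only side-effect rate in the documents is the Background's figure of more than 77% overall on magnesium, which is not split by effect, arm or baseline status. The following are therefore assumptions:
- new-onset rates p of 10% (standard) and 50% (alternate);
- baseline prevalence b of 20%, 30% or 40%, equal in the two arms;
- a symptom present at baseline persists.

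**Formulas.**
- Raw post-dose prevalence: b + (1-b)p. Difference between arms: (1-b) × (50% - 10%).
- New onset over all randomized women: (1-b)p. The difference is the same as above, but both proportions are lower.
- New onset among women free of the symptom at baseline: p. The full 40-point difference is kept, with about 18(1-b) women per arm.

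Example at b = 30%: raw prevalence is 0.30 + 0.70 × 0.10 = 37% versus 0.30 + 0.70 × 0.50 = 65%, a difference of 28 points. New onset over all women is 0.70 × 0.10 = 7% versus 0.70 × 0.50 = 35%, also 28 points.

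**Power** (exact Fisher test, two-sided 5%; the last column averages over the chance number of women free of the symptom):

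| b | Raw prevalence | Power, raw | New onset, all women | Power | Expected women per arm free at baseline | Power, those women only |
|---|---|---|---|---|---|---|
| 0% | 10% v 50% | 67% | 10% v 50% | 67% | 18 | 67% |
| 20% | 28% v 60% | 40% | 8% v 40% | 51% | 14.4 | 58% |
| 30% | 37% v 65% | 31% | 7% v 35% | 42% | 12.6 | 51% |
| 40% | 46% v 70% | 23% | 6% v 30% | 34% | 10.8 | 42% |

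**Sensitivity.** With assumed new-onset rates of 20% versus 60%, at b = 20%, 30% and 40%:
- raw prevalence: 40%, 31%, 23%;
- new onset over all women: 42%, 34%, 27%;
- new onset among women free at baseline: 50%, 45%, 38%.

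The direction is the same. The gain with all women in the denominator is small here, so the choice of denominator matters.

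**Vital signs.** Respiratory rate, oxygen saturation, blood pressure and heart rate are listed as measurements. In randomized arms, the expected difference in means is unbiased with or without baseline. Adjusting for a pre-dose value with correlation r removes a fraction r² of the residual variance: 16% at r = 0.4 and 36% at r = 0.6, both assumed.

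**The case against.** The strongest reply is that the documents do not state a wrong rule. Aim 2 is one sentence, not an endpoint definition. To call something a side effect already implies attribution to the drug, and naming only post-dose times is a natural way to describe a drug effect. This stands in part. A reader might infer that the plan scores every finding present after dosing as a magnesium effect, but no section says so. The counting rule is absent, and raw prevalence is only where the wording leads.

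Four other strong readings also fail:
- **That raised blood pressure at entry dilutes the comparison.** The vital signs have no cut-offs. Compared as values, they lose precision only.
- **That a chance baseline imbalance would be mistaken for a drug effect.** A valid test already allows for chance imbalance. Using baseline improves precision but does not repair the error rate.
- **That a null Aim 2 would lead to adoption of the larger regimen.** No section contains such a decision rule.
- **That the fix restores 67% power.** That is the power when nobody has the symptom beforehand, not the power after the fix.

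It is also fair to say that flushing and reflex depression may be rare before magnesium. For them b is near zero and little changes.

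**Conclusion.** The point holds in a limited form. Aim 2 is framed on post-dose frequency, an implied pre-dose assessment has no stated use, and the only model is for serum magnesium. For yes/no symptoms that can precede treatment, raw prevalence would shrink the difference by (1-b) and lower power. At b = 30%, with 10% versus 50% new onset assumed, power is 31%, against 42% to 51% when new onset is counted, a gain of 11 to 20 percentage points. The direction follows from the algebra if baseline symptoms persist. The size rests wholly on assumed rates, and under the second set of rates it is smaller (31% against 34% to 45%). The vital signs lose precision only. This is a secondary aim and the remedy is inexpensive, so the change should be made. It does not undermine Aim 1.

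**What to change.** - **Section 2:** state outright that side effects are recorded at the pre-dose draw.
- **Specific Aim 2 and Section 4:** define each symptom and reflex depression as new or worsened since that assessment. State whether the denominator is all randomized women or those free of the effect at baseline. Compare the arms at each of the three times.
- **Vital signs:** analyze the four as values adjusted for the pre-dose value, not as effects that are more or less common.
- **Open assessment:** the plan says that "it is not blinded and both the investigator and the research subject may know what dose of magnesium sulfate is being administered". It is therefore safer to derive new or worsened status from the two recorded readings than from the assessor's judgement.

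The cost is wording and a little more analysis, with no extra visits or samples. Worsening can be derived only if the form records a grade; with a yes/no entry, only new onset is available. Restricting to women free of the effect at baseline keeps the full difference but leaves fewer women (about 12.6 of 18 per arm at b = 30%).

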## Background

Magnesium sulfate is one of the most commonly prescribed intravenous medications in contemporary obstetric practice. Magnesium is the drug of choice for preventing seizures in women with preeclampsia, a leading cause of maternal morbidity and mortality. More than 77% of expectant mothers experience side effects related to antenatal magnesium administration. Magnesium may also negatively impact obstetric outcomes and lead to adverse neonatal effects. Current intravenous magnesium treatment for various indications (preeclampsia, tocolysis, neuroprotection) follows standardized protocols (4-6 g loading dose followed by an infusion at 1-2 g/h) based on institution preference. These protocols proposed by Prichard in 1979 were derived clinically to provide estimated serum magnesium levels necessary to treat eclamptic seizures. These standardized protocols are administered unaltered to all patients, without adjustment for maternal or fetal factors that may affect serum magnesium levels. The PI has previously constructed a detailed, robust pharmacokinetic (PK) model of intravenous magnesium sulfate administered antenatally to expectant mothers and exposed fetuses with the aim of optimizing maternal and fetal outcomes while preventing maternal and neonatal overdosing and morbidity associated with current magnesium treatment protocols.

The PK data derived from this pilot study at another academic institution suggests obese pregnant women may require an increased dose of magnesium sulfate to maintain a therapeutic serum level for prevention of eclamptic seizures ( $\geq 4.8$  mg/dL). In that pilot study, statistical modeling suggested more obese preeclamptic women take approximately twice as long as non-obese preeclamptic women to achieve steady state levels of the drug.

## **Study Design**

The proposed study would use 1:1 allocation to randomize women with a  $\text{BMI} \geq 35 \text{ kg/m}^2$  treated with magnesium sulfate for preeclampsia to either standard dosing of the drug at OHSU (4g loading dose, followed by a 1 g/hr infusion) or to increased dosing (6g loading dose, followed by a 2 g/hr infusion). Maternal serum magnesium levels will be obtained at baseline, as well as after administration of magnesium sulfate at 1 hour, 4 hours, and at the time of delivery (within 20 minutes). We will exclude patients who are  $< 32$  weeks gestation, as these women will automatically be administered a 6g loading dose, followed by 2g/hr infusion for fetal neuroprotection. The outcome will be a comparison of the proportion of preeclamptic women in each magnesium sulfate protocol group who have therapeutic serum levels 4 hours after administration, and at the time of delivery (serum magnesium level of  $\geq 4.8$  mg/dL). We hypothesize that a significantly higher proportion of women with a  $\text{BMI} \geq 35 \text{ kg/m}^2$  will be subtherapeutic at 4 hours and at the time of delivery when administered standard dosing of magnesium sulfate. Findings from the proposed research can be used to tailor treatment for preeclampsia in obese pregnant patients.

## **Study Population**

Pregnant women between 32-42 weeks' gestation who are prescribed magnesium sulfate for preeclampsia.

## **Number of Subjects**

Based on a previous retrospective study conducted by Tudela et al and our own pilot data, we estimate that 50% of obese women will be subtherapeutic for eclamptic seizure prophylaxis 4 hours after magnesium sulfate administration. Assuming 95% of normal weight women have therapeutic serum magnesium levels after 4 hours of administration, we anticipate that 18 patients (36 total) are needed in each dosing group to detect a 50% difference in the proportion of women with a  $\text{BMI} \geq 35 \text{ kg/m}^2$  who have therapeutic magnesium levels 4 hours after magnesium sulfate administration. Based on current patient load, which includes treatment of approximately 40 preeclamptic patients per month, and the additional inclusion criteria of the disease severity requiring magnesium sulfate administration, as well as a maternal  $\text{BMI} \geq 35 \text{ kg/m}^2$ , and anticipated number of patients declining study participation, we anticipate potential enrollment of 1-2 women and their neonates per week.

### **a. Inclusion and Exclusion Criteria**

Pregnant women with preeclampsia admitted to OHSU hospital will be screened for eligibility using the institution's electronic medical record – EPIC, on admission.

Inclusion criteria:

Pregnant women who are ages 15 - 45

32-42 weeks' pregnant

Prescribed magnesium sulfate for preeclampsia

BMI  $\geq$  35 kg/m^2

Exclusion criteria:

Pregnant women < 32 weeks' pregnant

Women who are on dialysis

Women with pre-existing renal disease

Data collected in the course of a screen failure will be destroyed immediately.

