**d. Recruitment Methods**

When pregnant women with preeclampsia are identified at presentation to OHSU hospital through review of the medical record, the PI and research staff will screen for participation based on maternal age, gestational age, and whether or not magnesium sulfate will be prescribed as part of usual care.

Assistance with the initial screening process will take place through resident education sessions, as well as posting of study inclusion/exclusion criteria in the resident workroom as a reminder. A study factsheet and recruitment flyer will be posted on Labor and Delivery, Antepartum, and in the resident workroom to facilitate enrollment. Recruitment outside of these areas is not anticipated due to the specific circumstances in which a potential research subject would qualify for enrollment (i.e. inpatient). Additionally, a recruitment Grand Rounds will be presented to the Department of OB/GYN to educate them regarding the study enrollment criteria.

There will be no payment for participation in the study, however, laboratory studies requested for subjects that would not have normally been requested as part of usual care (i.e. blood, urine, and cerebrospinal fluid magnesium levels), will not be charged to the subject.

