### e. Consent Process

Once a potential participant has been identified, the PI or appropriate research staff will approach potential participants for consent while standard laboratory workup ensues for preeclampsia. Written informed consent will be obtained after having the purpose and details of the study explained in person by the PI or other research personnel. Because study participation is limited to inpatients who are prescribed the study drug, no outside recruitment of subjects will take place.

After explaining the purpose of the study, the process of randomization, and obtaining informed consent, the PI /research personnel will use a random number generator from OpenEpi to assign the patient to one of two magnesium sulfate dosing regimens.

The PI/research personnel will review the list of daily obstetric service patients to identify possible participants for recruitment.

During the consent process, it will be emphasized to the potential research subject that the study drug is given in varying doses at different institutions and that if they choose not to participate, they will receive the dose that is standardly prescribed at OHSU for preeclampsia.

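### The renal exclusion does not clearly cover impairment arising with the current preeclampsia, and no renal result has to be reviewed before a woman is randomized to the larger dose

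*Combined protocol and SAP*

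**What the plan says.** All places are in the combined protocol and SAP.

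- **Eligibility.** The section on inclusion and exclusion criteria has two renal exclusions: dialysis, and "Women with pre-existing renal disease". It gives no creatinine limit and no criterion worded for acute kidney injury.
- **Timing.** Under Consent Process, staff "will approach potential participants for consent while standard laboratory workup ensues for preeclampsia". The assignment is generated after consent. No laboratory result is named as a condition.
- **Baseline visit.** The visit table in Procedures Involved lists "Consent Discussion, Screening tests and medical history" at Visit 1. It does not name the tests or set a threshold.
- **Dose outside the trial.** Women who decline are told that "they will receive the dose that is standardly prescribed at OHSU for preeclampsia". Study Design gives that dose as a 4 g load and then 1 g/h.
- **Dose in the alternate arm.** Procedures Involved specifies "a starting dose of magnesium sulfate of 6g, followed by 2g every hour until 24 hours after delivery".
- **Safeguards after dosing starts.** "If the subject is found to be symptomatic at any point in the study, the usual clinical care will be provided", which includes a magnesium level and a dose reduction if needed. Risks to Subjects allows the drug to be stopped or changed for serious side effects. Magnesium levels and side effects, including reflexes, respiratory rate and oxygen saturation, are taken at 1 hour, 4 hours and delivery.

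**The concern.** The plan already keeps women with established renal disease out of a dose comparison. The same caution is not clearly extended to renal function that has fallen during the illness for which these women are being treated. Consent and assignment can both be completed while the laboratory workup is still in progress, so staff following the written steps need not have seen a renal result when the dose is drawn.

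This is a question of individual safety. For such a woman, joining the trial is what opens the route to the larger starting regimen. If she declines, she receives the smaller one.

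**Working it through.** The plan gives no figure on this point to reproduce. Its one calculated figure, 18 women per group, does not enter the argument. The check is a reading of the text followed by simple dose arithmetic.

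**1. Does any provision close the gap before assignment?**

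- Exclusions: pre-existing disease and dialysis only. The reference point for pre-existing is not stated.
- Visit 1 tests: a creatinine may be among them, but a test with no limit and no required review does not decide eligibility.
- Consent Process: the stated precondition for assignment is explanation and informed consent.

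So nothing in the plan makes a renal result a condition of assignment.

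**2. Does any provision tie a later result to a dose change?**

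The written triggers are symptoms (Procedures Involved) and serious side effects (Risks to Subjects). Magnesium is measured on schedule, but no level is set at which the dose must change. Sharing of Results promises providers the usual-care results. Recruitment Methods gives blood magnesium as an example of a test that usual care would not normally include. The plan therefore does not commit clinicians to act on the scheduled levels, although it does not say that those levels are withheld.

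**3. Size of the difference in starting exposure**

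Inputs: 4 g plus 1 g/h and 6 g plus 2 g/h (Study Design). Cumulative dose at *h* hours = load + rate × *h*, with maintenance counted from time 0 and no dose change.

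- 1 hour: 6 + 2 × 1 = 8 g against 4 + 1 × 1 = 5 g.
- 4 hours: 6 + 2 × 4 = 14 g against 4 + 1 × 4 = 8 g. The difference is 6 g and the ratio is 14/8 = 1.75.

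Maintenance follows the load, and the plan does not say how long the load takes. If it took 1 hour (an assumption), maintenance would run for 3 of the 4 hours: 6 + 2 × 3 = 12 g against 4 + 1 × 3 = 7 g, a difference of 5 g and a ratio of 1.71. The time-0 convention therefore slightly overstates the totals but hardly alters the contrast.

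Under 1:1 allocation, an enrolled woman with acute impairment has a 50% chance of the larger regimen.

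**4. What cannot be computed**

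The documents give no rate of acute renal impairment in this population, and no serum level or toxicity figure for either regimen in such women. The number of women affected and the harm per woman are not estimated.

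**The case against.** The strongest reply is that the plan is less exposed than it looks. Much of this stands, and it limits what can be claimed.

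- **Both regimens are familiar.** Drugs or Devices says both are already used at this hospital, and Study Design says women under 32 weeks receive the larger one automatically. That makes the exposure less novel, but neither section speaks to renal function.
- **Care is open-label and responsive.** A reader might infer that randomization, and not renal function, fixes a woman's dose throughout. The plan does not support that, because the dose can be reduced at any point if she is symptomatic. The claim holds for the starting regimen only. Nor would renal function necessarily set the dose outside the trial, since Background describes standard protocols as given without adjustment.
- **Pre-existing is ambiguous.** It could be read as present before study drug, which would include impairment found on admission. The fair statement is that acute impairment is not clearly covered.
- **The recruitment list is not the full screen.** Recruitment Methods describes screening "based on maternal age, gestational age, and whether or not magnesium sulfate will be prescribed as part of usual care". A reader might infer that renal status goes unchecked. But the list also omits BMI, dialysis and pre-existing renal disease, all of which the eligibility section requires, so it shows nothing about renal screening in particular.
- **Chart abstraction.** The items include "renal function and creatinine clearance (if available". It is tempting to conclude that renal function itself is optional. The qualifier most naturally belongs to creatinine clearance. Likewise, the sentence on covariates that may affect dosing refers to the whole list and does not single out a renal hazard.

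What survives is narrower: the exclusion is unclear on acute impairment, and no result gates the assignment. None of these replies supplies either safeguard.

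**Conclusion.** The point holds as a safety gap at entry. Under the steps as written, a woman with renal impairment arising with her preeclampsia could start on 6 g plus 2 g/h when she would have had 4 g plus 1 g/h outside the trial. That is 14 g against 8 g by 4 hours, assuming maintenance from time 0 and no dose change. The later safeguards are real but act after dosing starts.

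Two stronger readings should be resisted. The gram totals are the ordinary contrast between the arms for any participant; they do not measure renal harm. Nor is the primary comparison biased, because eligibility is settled before random assignment and applies alike to both arms. The gap is worth closing before enrolment because the remedy is specific and cheap, but it does not undermine the trial.

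**What to change.** Three wording changes:

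1. In the exclusion criteria, replace the renal disease item with: pre-existing renal disease, or admission serum creatinine above a limit the investigators fix before first enrolment.
2. In Consent Process, generate the assignment only after that result has been reviewed. A woman whose magnesium is ready first is not enrolled and receives usual care. The section on non-English speaking subjects already applies this principle when the drug is ready before consent, so treatment is not delayed.
3. In Procedures Involved, record the admission creatinine for every enrolled woman.

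**Cost.** No new test is needed if creatinine is already part of the standard preeclampsia workup, which should be confirmed. Some women will be lost to late or raised results. The plan expects 1 to 2 enrolments per week, so 36 women take 36/2 = 18 to 36/1 = 36 weeks. For assumed losses among women who would otherwise have enrolled:

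- 5%: 36/0.95 = 37.9, about 2 more women and 1 to 2 more weeks.
- 10%: 36/0.90 = 40, 4 more women and 2 to 4 more weeks.
- 20%: 36/0.80 = 45, 9 more women and 4.5 to 9 more weeks.

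The true loss is not in the documents. Results would not apply to women with acute renal impairment. The gate acts only at entry, so a woman whose renal function worsens after assignment still depends on the existing safeguards.
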